- I will provide copies of the protocol and all pertinent information to all individuals responsible to me who assist in the conduct of this study. I will discuss this material with them to ensure they are fully informed regarding the conduct of the study.

I will ensure that the Institutional Review Board (IRB) / Ethics Committee (EC) review complies with governmental requirements and will be responsible for the initial and continuing review and approval of the clinical investigation. I also agree to promptly report to the IRB/EC all changes in the research activity and all unanticipated problems involving risks to human subjects or others. Additionally, I will not make any changes in the research without Sponsor and IRB/EC approval of an amended protocol, except where necessary to eliminate apparent immediate hazards to human subjects.

I agree to comply with all other requirements regarding the obligation of clinical Investigators and all other pertinent requirements of the Sponsor and government agencies.

Signature of Principal Investigator (PI)

Date

Printed Name of PI

CLINICAL STUDY PROTOCOL SYNOPSIS

Regulatory Phase:
	
Post-Market Clinical Follow-Up

Indication:
	
The ENSEAL® X1 Large Jaw Tissue Sealer instrument (ENSEAL X1) is a dedicated bipolar electrosurgical instrument intended for use in open surgical procedures where ligation and division of vessels is desired. It is a bipolar instrument for use with the Ethicon Generator G11 (GEN11). It is intended for use during open surgery to cut and seal vessels, cut, grasp, and dissect tissue during surgery. Indications for use include open general, gynecologic, urologic, thoracic, and vascular procedures. These procedures include hysterectomies, colectomies, Nissen fundoplication, adhesiolysis, oophorectomies, etc. The devices can be used on vessels (arteries, veins, pulmonary vasculature, lymphatics) up to and including 7 mm and tissue bundles.

Objective(s):
	
The primary objective of this study is to prospectively generate device-specific clinical data related to hemostasis in a post-market setting using the ENSEAL X1 per its instructions for use (IFU). Secondary objectives include proactive surveillance of safety and performance outcomes following use of the ENSEAL X1.


Overview of Study Design:
	
This prospective, single-arm, multi-center, evaluation will collect clinical data in a post-market setting. The three types of procedures studied will be colectomy, gynecological, and thoracic. Investigators will perform each procedure using the device in compliance with their standard surgical approach and the ENSEAL X1 IFU. There will be no blinding or planned interim analysis in this study.
 
Each site will utilize consecutive screening and enrollment in an effort to generate a random and representative patient population sample. Subjects will be consented and screened anytime between the time of scheduling the procedure and hospital admission (this period will vary per subject but may occur over several dates within an 8-week period prior to surgery). Subjects will be considered enrolled at the time of the first attempted vessel transection using the ENSEAL X1 device during their procedure for purposes of this study. The last study visit will be at the post-op follow-up visit at approximately 4 weeks; therefore, from the surgery date to study exit, the duration will be approximately four weeks and the total study participation can be up to 12 weeks.

Number of Subjects:
	
A total of 100 eligible subjects are planned to be enrolled in up to 8 sites with the following procedure targets (each site will utilize consecutive screening and enrollment):
 
 • Minimum of 30 subjects enrolled for colectomy procedures (e.g., total colectomy, partial colectomy, hemicolectomy, proctocolectomy); • Minimum of 30 subjects enrolled for gynecological procedures (e.g., hysterectomy); • Minimum of 20 subjects enrolled for thoracic procedures (e.g.,

	
esophagectomy); and
 
The remaining 20 subjects will be enrolled from any of the procedure groups (colectomy, gynecological, or thoracic).

Criteria for Inclusion:	
Subjects satisfying the following criteria will be considered eligible for enrollment in this study:
 
 1. Elective procedure (colectomy, gynecological, or thoracic) where at least one vessel is planned to be transected by the ENSEAL X1 device per its IFU; 2. Willingness to give consent and comply with all study-related evaluations and treatment schedule; and 3. At least 18 years of age.
Criteria for Exclusion:	
Subjects meeting any of the following criteria will be considered not eligible for enrollment in this study:
 
 1. Physical or psychological condition which would impair study participation; or 2. Enrollment in a concurrent clinical study.
Test Product:	
ENSEAL X1 Large Jaw Tissue Sealer (Product Code: NSLX120L) and Ethicon Endo-Surgery Generator G11

Reference Therapy/Product:	
No comparator product is being used in this study.

Duration of Treatment:	
Subjects will be exposed to the ENSEAL X1 device during the procedure they undergo and while the device is used as indicated in the IFU.

Criteria for Evaluation:	
Primary performance endpoint:
 
 • Percentage of vessels where hemostasis (\leq Grade 3) is achieved using the ENSEAL X1 and no additional hemostatic products (e.g., hemoclips, staples, sutures, fibrin sealants, other advanced energy) are needed to obtain hemostasis. Hemostasis grading scale: 
 ○ Grade 1: no bleeding at transection site; ○ Grade 2: minor bleeding at transection site, no intervention needed; ○ Grade 3: minor bleeding at transection site, mild intervention needed, use of monopolar device and/or touch-ups with ENSEAL X1; ○ Grade 4: significant bleeding (e.g., pulsatile blood flow, venous pooling) requiring intervention such as extensive coagulation or ligation with additional hemostatic products (e.g., hemoclips, staples, sutures, fibrin sealants, other advanced energy products). 
Secondary performance endpoints:
 
 • Hemostasis grading assessment for each vessel transection;

	
 • Incidence of requirement (number of times and reason for use) for ENSEAL X1 touch-ups for Grade 3; • Incidence of requirement (type, name of product, and number of times) for additional hemostatic products for Grade 4 interventions (e.g., hemoclips, staples, sutures, fibrin sealants, other advanced energy products) to obtain hemostasis on vessels; 
Primary safety endpoint
 
 • Safety will be assessed through summarization of all device-related adverse events (AEs). Adverse events will be assessed for seriousness, severity, action taken, and outcome. 
Other key data collected:
 
 • Surgical procedure conducted; • Procedure duration; • Hospital stay duration; • Name and number of vessels that were transected; • Incidence and location of cancer and occurrence of pre-surgical radiation/chemotherapy, if applicable (when and how many doses); • Occurrence of vessel skeletonization; • Presence of inflamed tissue or calcified tissues/vessels, if applicable; • Volume of estimated intra-operative blood loss; • Date(s) of chest tube placement and removal, if applicable; • Daily volume and characteristics of chest tube(s) drainage, if applicable; • Occurrence of ENSEAL X1 used for tissue cutting or dissection (description of tissue cut/dissected); • Procedure-related AEs; and • Device and Surgeon questionnaires.

Statistical Analysis:
	
Analysis Sets
 
The summary of all performance and safety endpoints will be performed on the set of subjects in whom the ENSEAL X1 device is utilized during the surgical procedure. The summary of all primary and secondary performance endpoints will be performed by procedure group (colectomy, gynecological, or thoracic). The summary of all safety endpoints will be performed by procedure group and on the entire pooled set of subjects.
 
Sample Size Determination
 
A sample size of 100 subjects is planned for enrollment in this study. No formal hypothesis is being tested in this study, thus the sample size was not statistically sized, but rather is considered sufficient for a descriptive summary of performance endpoints within each procedure group. It is expected that at least 2 vessels will be transected within each procedure, providing an expected minimum of at least 60 transections within colectomy and gynecological procedure groups and at least 40

transections in the thoracic procedure group for a total of at least 200 transections.

From a safety perspective on the pooled analysis of 100 subjects and in consideration of rare AEs that may occur (e.g., bleeding requiring blood product transfusion), for an event that has an incidence rate of, for example, 2%, then in a sample of 100 subjects, the probability of observing at least 1 event is 86.7% under a binomial probability model. Thus, this sample size provides a high probability of observing rare events if they do occur, and provides reasonable assurance to conclude that the likelihood of such AEs is less than 3.7% if they do not occur based on the upper limit of an exact 95% confidence interval when 0 events out of 100 subjects are observed.

Performance Analyses

The number and percentage of vessels where hemostasis is achieved (\leq Grade 3) will be summarized and a 95% confidence interval will be estimated for each procedure group (colectomy, gynecological, or thoracic). Counts and percentages will be provided for type, size, and number of vessels transected, summary of grading scale distribution for all vessels transected, number of times ENSEAL X1 touch-ups were required, and incidence of requirement for additional measures to obtain hemostasis on vessels (other advanced energy devices or hemostatic products).

Safety Analyses

All device-related and procedure-related AEs reported during the study will be coded to the Medical Dictionary for Regulatory Activities (MedDRA). All AEs will be summarized by MedDRA system organ class and preferred term by procedure group and in total. Separate summaries will be provided for device-related and procedure-related AEs. Serious AEs will be summarized in a similar manner.

TABLE OF CONTENTS

	Page
PROTOCOL SIGNATURE PAGE.....	2
INVESTIGATOR SIGNATURE PAGE.....	3
CLINICAL STUDY PROTOCOL SYNOPSIS.....	4
PROTOCOL-SPECIFIC ACRONYMS AND ABBREVIATIONS.....	10
ETHICS.....	11
ADMINISTRATIVE REQUIREMENTS.....	12
1.0 INTRODUCTION.....	13
2.0 STUDY OBJECTIVES.....	13
2.1 Primary Performance Endpoint.....	13
2.2 Secondary Performance Endpoints.....	13
2.3 Primary Safety Endpoint.....	14
2.4 Additional Key Data Collected.....	14
3.0 INVESTIGATIONAL PLAN.....	14
3.1 OVERALL STUDY DESIGN AND PLAN - DESCRIPTION.....	14
3.2 STUDY POPULATION.....	15
3.2.1 Enrollment.....	15
3.2.2 Screening Failures.....	15
3.2.3 Inclusion Criteria.....	15
3.2.4 Exclusion Criteria.....	15
3.2.5 Removal of Subjects from Study.....	15

	APPENDIX I – VESSEL SEALING ASSESSMENT	31
	APPENDIX II – DEVICE PROCEDURE QUESTIONNAIRE	32
	APPENDIX III – SURGEON QUESTIONNAIRE	33
	APPENDIX IV – ANTICIPATED ADVERSE EVENTS	35

PROTOCOL-SPECIFIC ACRONYMS AND ABBREVIATIONS

Acronyms/Abbreviations	Terms
AE	Adverse event
CFR	Code of Federal Regulations
EC	Ethics committee
eCRF	Electronic case report form
EDC	Electronic Data Capture
EES	Ethicon Endo-Surgery, Inc.
ENSEAL X1	ENSEAL® X1 Large Jaw Tissue Sealer
GEN11	Ethicon Endo-Surgery Generator G11
FDA	Food and Drug Administration
GCP	Good clinical practice
ICD	Informed consent document
IFU	Instructions for use
IRB	Institutional review board
MedDRA	Medical Dictionary for Regulatory Activities
OR	Operating room
PCF	Product complaint form
PHI	Protected health information
PI	Principal Investigator
PMCF	Post-market clinical follow-up
SAE	Serious adverse event
SAP	Statistical analysis plan
SOC	Standard of care

ETHICS

Institutional Review Board/Ethics Committee

Participating investigators will ensure that this protocol, Informed Consent Document (ICD), ICD or protocol amendments, and if applicable, any other written information provided to the subjects that assist in the decision to participate are reviewed by an Institutional Review Board (IRB) or Ethics Committee (EC) that complies with governmental requirements. The approving IRB/EC will be responsible for the initial and continuing review and approval of this clinical investigation. Participating investigators will be required to promptly report to the IRB/EC as required by the IRB/EC's policies. Additionally, investigators will be required to refrain from making any changes in the clinical investigation plan without Sponsor and IRB/EC approval of an amended protocol, except where necessary to eliminate apparent immediate hazards to study subjects or others.

Applicable Regulations

This study will be conducted in compliance with GCP and in accordance with the Declaration of Helsinki, as well as any other applicable local and country regulatory requirements.

Subject Information and Consent

Regulations concerning the protection of subjects require that informed consent be obtained before a subject may participate in any clinical investigation. An IRB/EC approved informed consent must be sought from each subject and must be appropriately documented in the subject's medical record prior to initiating the study. It is the Investigator's responsibility to obtain written informed consent from the subject, the Investigator may delegate this responsibility if appropriately documented.

The informed consent process involves the following: giving a subject adequate information concerning the study, providing adequate time for the subject to consider all available options, responding to the subject's questions, ensuring that the subject has comprehended this information and finally, obtaining the subject's written consent to participate in this study. All subjects in this study should be completely informed about the purpose, risks, benefits, and other pertinent details of this study. The informed consent process is careful to avoid the perception of any coercion or undue influence on, or inducement of, the subject to participate, and does not waive or appear to waive the subject's legal rights. The ICD is presented in native, non-technical language that is understandable to the subject.

Prior to a subject's participation in this study, an ICD will be signed and dated by the subject and person who conducted the consent discussion. The subject will be provided a copy of the signed ICD. The ICD and any other written materials provided to the subject to assist in the decision to participate must be revised whenever new information becomes available that may be relevant to their willingness to participate or continue participation in this study. Revision to the ICD and other written materials will receive IRB/EC approval before implementation. Each subject will be required to sign any amended ICD (as required by the IRB/EC) and will receive a copy of the signed ICD.

ADMINISTRATIVE REQUIREMENTS

This study is sponsored by Ethicon Endo-Surgery, Inc. (EES, Cincinnati, OH, USA) and will be conducted in up to eight surgery centers in the United States and/or European Union under a single protocol approved by each participating site's IRB/EC prior to implementation. The principal investigator at each study site is a surgeon qualified by education, experience, and training to perform the study procedure and to assume responsibility for the conduct of this study.

The Data Management and Biostatistics groups of the Sponsor will be responsible for the analysis of data from this protocol. An Electronic Data Capture (EDC) system will be utilized by study site personnel to transfer study data from source records (the first point of clinical data capture) onto common electronic case report forms (eCRFs). This system is a web-based, secure electronic software application (

Protocol Modifications

All protocol amendments must be issued by the Sponsor, signed and dated by the Investigator, and should not be implemented without prior IRB/EC approval, except where necessary to eliminate immediate hazards to the subjects or when the change(s) involves only logistical or administrative aspects of the study (e.g., change in monitor(s), change of telephone number(s)). The Investigator reports the protocol amendments to the IRB/EC as per their local requirements.

1.0 INTRODUCTION

The ENSEAL® X1 Large Jaw Tissue Sealer instrument (ENSEAL X1) is a dedicated bipolar electrosurgical instrument intended for use in open surgical procedures where ligation and division of vessels is desired. It is intended for use during open surgery to cut and seal vessels, cut, grasp, and dissect tissue during surgery. Indications for use include open general, gynecologic, urologic, thoracic, and vascular procedures.

Many of the benefits realized by the ENSEAL X1 are tied to the ergonomics of the device. The ENSEAL X1 has simplified the steps for use as compared to the ENSEAL® Super Jaw device. The device has separate seal and cut functionality, a 360° single hand rotation of the device shaft, a uniform compression system that reduces the potential for end effector damage, and steps for use that are intuitive for the user.

This study will specifically look at the use of ENSEAL X1 in colectomy, gynecological, and thoracic procedures.

2.0 STUDY OBJECTIVES

The primary objective of this study is to prospectively generate device-specific clinical data related to hemostasis in a post-market setting using the ENSEAL X1 per its IFU. Secondary objectives include proactive surveillance of safety and performance outcomes following use of the ENSEAL X1.

2.1 PRIMARY PERFORMANCE ENDPOINT

The primary performance endpoint in this study is the percentage of vessels where hemostasis (\leq Grade 3) is achieved using the ENSEAL X1 and no additional hemostatic products (e.g., hemoclips, staples, sutures, fibrin sealants, other advanced energy) are needed to obtain hemostasis. Hemostasis grading scale:

- Grade 1: no bleeding at transection site;
- Grade 2: minor bleeding at transection site, no intervention needed;
- Grade 3: minor bleeding at transection site, mild intervention needed, use of monopolar device and/or touch-ups with ENSEAL X1;
- Grade 4: significant bleeding (e.g., pulsatile blood flow, venous pooling) requiring intervention such as extensive coagulation or ligation with additional hemostatic products (e.g., hemoclips, staples, sutures, fibrin sealants, other advanced energy products).

2.2 SECONDARY PERFORMANCE ENDPOINTS

The secondary performance endpoints in this study are:

- Hemostasis grading assessment for each vessel transection;
- Incidence of requirement (number of times and reason for use) for ENSEAL X1 touch-ups for Grade 3; and
- Incidence of requirement (type, name of product, and number of times) for additional hemostatic products for Grade 4 interventions (e.g., hemoclips, staples, sutures, fibrin sealants, other advanced energy products) to obtain hemostasis on vessels.

2.3 PRIMARY SAFETY ENDPOINT

The primary safety endpoint in this study is the summarization of all device-related AEs. Adverse events will be assessed for seriousness, severity, action taken, and outcome.

2.4 ADDITIONAL KEY DATA COLLECTED

Additional key data collected in this study are:

- Surgical procedure conducted;
- Procedure duration;
- Hospital stay duration;
- Name and number of vessels that were transected;
- Incidence and location of cancer and occurrence of pre-surgical radiation/chemotherapy, if applicable (when and how many doses);
- Occurrence of vessel skeletonization;
- Presence of inflamed tissue or calcified tissues/vessels, if applicable;
- Volume of estimated intra-operative blood loss;
- Date(s) of chest tube placement and removal, if applicable;
- Daily volume and characteristics of chest tube(s) drainage, if applicable;
- Occurrence of ENSEAL X1 used for tissue cutting or dissection (description of tissue cut/dissected);
- Procedure-related AEs; and
- Device and Surgeon questionnaires.

3.0 INVESTIGATIONAL PLAN

3.1 OVERALL STUDY DESIGN AND PLAN - DESCRIPTION

This prospective, single-arm, multi-center, evaluation will collect clinical data in a post-market setting. The three types of procedures studied will be colectomy, gynecological, and thoracic. Investigators will perform each procedure using the device in compliance with their standard surgical approach and the ENSEAL X1 IFU. There will be no blinding or planned interim analysis in this study.

Each site will utilize consecutive screening and enrollment in an effort to generate a random and representative patient population sample. Subjects will be consented and screened anytime between the time of scheduling the procedure and hospital admission (this period will vary per subject but may occur over several dates within an 8-week period prior to surgery). Subjects will be considered enrolled at the time of the first attempted vessel transection using the ENSEAL X1 device during their procedure. Procedures will be performed per each institution's standard-of-care (SOC) that is specific for each procedure group (colectomy, gynecological, and thoracic). The last study visit will be at the post-op follow-up visit at approximately 4 weeks. Follow-up by phone for subjects is allowed when an on-site visit is not planned.

3.2 STUDY POPULATION

3.2.1 Enrollment

Subjects will be recruited from the existing patient population who plan to have an elective procedure from the proposed procedure groups (colectomy, gynecological, and thoracic). All eligible subjects (Sections 3.2.3 and 3.2.4) will be considered enrolled at the time of the first attempted vessel transection using the ENSEAL X1 device during their procedure. Up to 8 centers (United States and Europe) will be selected as study sites. Each participating investigator is expected to perform a minimum of two procedures using the ENSEAL X1 device. A total of 100 eligible subjects are planned to be enrolled with a minimum of 30 subjects enrolled for colectomy procedures (e.g., total colectomy, partial colectomy, hemicolectomy, proctocolectomy), a minimum of 30 subjects enrolled for gynecological procedures (e.g., hysterectomy), and a minimum of 20 subjects enrolled for thoracic procedures (e.g., esophagectomy). The remaining subjects will be enrolled from any of the three procedure groups and enrollment will be competitive between procedure groups and the remaining 20 subjects.

3.2.2 Screening Failures

All subjects signing consent who do not have at least one vessel transection attempted by ENSEAL X1 during their procedures will be recorded as screen failures. For subjects who are determined to be screen failures, only the relevant electronic eCRF pages (inclusion/exclusion criteria, demographics, AEs, subject completion/discontinuation) will be completed.

3.2.3 Inclusion Criteria

Subjects satisfying the following criteria will be considered eligible for enrollment in this study:

1. Elective procedure (colectomy, gynecological, or thoracic) where at least one vessel is planned to be transected by the ENSEAL X1 device per its IFU;
2. Willingness to give consent and comply with all study-related evaluations and treatment schedule; and
3. At least 18 years of age.

3.2.4 Exclusion Criteria

Subjects meeting the following criteria will be considered not eligible for enrollment in this study:

1. Physical or psychological condition which would impair study participation; or
2. Enrollment in a concurrent clinical study.

3.2.5 Removal of Subjects from Study

In accordance with the current revision of the Declaration of Helsinki and the CFRs, a subject has the right to withdraw from the study at any time for any reason without prejudice to his/her future medical care by the physician or the institution. Should a subject (or subject's legally authorized guardian/representative) decide to withdraw, 1) all data collected up to the point of withdrawal will be considered for analysis; and 2) all efforts will be made to collect and report the final visit observations as thoroughly and timely as possible. Participation may be terminated prior to completing the study for any of the reasons listed below (reasons that do not fit the categories below will be documented as "other").

Adverse Event

When the subject experiences an AE and the Investigator or Medical Monitor believes it is in the best interest of the subject to discontinue participation in the study, the subject will be withdrawn from the study.

Lost to follow-up

When contact with the subject has been lost without completing a final contact assessment, and every attempt (3 times) to contact the subject has failed, the subject will be considered lost to follow-up. All attempts to contact the subject requesting his/her return for the final visit must be documented.

Withdrawal of consent

Any method of contact with the subject (or subject's legally authorized guardian/representative) in which he/she state they no longer want to participate in the study specific activities constitutes withdrawal of consent for participation in the study. When possible, the reason for withdrawal will be documented.

Site Termination or Study Termination

A study site or the entire study may be terminated. When this occurs, all subjects currently enrolled at the site will be withdrawn and documented as early terminations. Reasons for site or study termination may include, but are not limited to the following:

- Administrative concerns (e.g., inadequate subject enrollment, Investigator/institution non-compliance, change of business strategy, etc.);
- Safety Issues, including those due to non-compliance, which substantially affect the risk to benefit ratio of the study subjects at a site or for the study as a whole; or
- Regulatory Body Mandate(s).

The Investigator has the right to terminate the subject's participation at any time. Should this be necessary, procedures for termination will be provided by the Sponsor.

Death

- When possible, the cause of death will be documented.

Other (which may include)

- Investigator recommendation.

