5.2 REPORTING PROCEDURES FOR ADVERSE EVENTS

5.2.1 Recording Adverse Events

The Investigator will record all AEs (both AEs and SAEs) considered attributable (relationship of unlikely, possible, probable, causal relationship) to the study procedure or the ENSEAL X1 in the source documents and eCRF.

Standard medical terminology should be used when recording AEs. In addition, the following information should be recorded:

- Onset date;
- Resolution date or date of death;
- Severity of the event;
- Indication of whether the event is serious;
- Relationship of AE to the device used in the study;
- Relationship of AE to the study procedure;
- Action taken;
- Event status; and
- Was the event anticipated or not.

Data related to SAEs will be collected until the event resolution, or until the event is considered stable, or until all attempts to determine the resolution of the event are exhausted. All SAEs that are unresolved at study completion (or at the last visit completed for early withdrawal subjects) will be recorded as ongoing at study end.

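### Site or study termination ends AE follow-up in subjects already exposed to the device, and the commitment to obtain final-visit data covers neither termination nor AE withdrawal (Protocol 3.2.5)

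*Protocol*

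**What the plan says.** Protocol 3.2.1 fixes the point of enrolment: eligible subjects "will be considered enrolled at the time of the first attempted vessel transection using the ENSEAL X1 device during their procedure". SAP 1.2 uses the same definition. The synopsis entry on duration of treatment confines device exposure to the operation.

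Protocol 3.2.5 sets the removal rules. On closure of a site or of the study: "When this occurs, all subjects currently enrolled at the site will be withdrawn and documented as early terminations". One listed reason for closure is "Safety Issues, including those due to non-compliance, which substantially affect the risk to benefit ratio of the study subjects". The adverse-event paragraph leaves the decision to the Investigator or the Medical Monitor, and applies when one of them "believes it is in the best interest of the subject to discontinue participation in the study, the subject will be withdrawn from the study". The same section promises that every effort will be made to obtain final-visit observations, but that sentence opens with the case where the subject or a representative decides to withdraw.

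Protocol 5.2.1 has two sentences on SAEs. The first reads "Data related to SAEs will be collected until the event resolution, or until the event is considered stable", and adds a third end point, when attempts to learn the outcome are exhausted. The second, on status when the study closes, reads "All SAEs that are unresolved at study completion (or at the last visit completed for early withdrawal subjects) will be recorded as ongoing".

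The Schedule of Events (Protocol 3.5) places AE assessment at the procedure-through-discharge visit and at Visit 3 (28 ± 14 days, office or telephone). Withdrawn subjects are not replaced (3.2.6), and nothing is imputed (Protocol 4.5.9.6, SAP 8.7).

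**The concern.** Once the operation is over, study participation consists almost entirely of safety follow-up. A rule that withdraws enrolled subjects when a site closes for safety reasons removes no exposure. It removes observation from people who have already been exposed, at the moment when observation is most informative. The existing final-visit commitment would address this, but it is tied to the subject's own decision. A subject who chooses to leave is pursued for a last assessment; for one removed by a site closure or because of an AE, the protocol makes no such promise.

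At stake is the primary safety endpoint, device-related AEs (Protocol 2.3, SAP 8.5), which are also to be assessed for outcome. The AE tables are counts and percentages on the ENSEAL Analysis Set, with no adjustment for time at risk. A subject whose follow-up ends early still counts in the denominator and appears free of any later event. Because the cut-off can be caused by a safety problem, the loss can be informative.

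**Working it through.** **Text, step by step**

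1. Enrolled means that a transection with the device has been attempted (3.2.1). Subjects currently enrolled at a closing site are therefore subjects in whom device use was attempted.
2. Exposure is limited to the operation. After discharge the only scheduled AE assessment left is Visit 3 (3.5). Withdrawal before Visit 3 removes that assessment and nothing else that is scheduled.
3. The final-visit commitment in 3.2.5 has one stated trigger, a decision by the subject or representative. Neither the AE paragraph nor the termination paragraph refers to it.
4. Section 5.2.1 continues data collection for SAEs already reported. It sets no comparable rule for non-serious AEs, and it cannot capture an event that first appears after contact has ended.
5. SAP Table 1 shows discontinuations by reason, but SAP Tables 14 to 19 do not carry them into the AE denominators.

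**The plan's own safety figures** (Protocol 4.5.7, SAP 7)

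Inputs: n = 100, true incidence 2%, exact two-sided 95% interval.

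- P(at least 1 event) = 1 − 0.98^100 = 0.867. Stated 86.7%; reproduced.
- Upper limit with 0 events = 1 − 0.025^(1/100) = 3.62%. Stated as less than 3.7%; consistent.

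Both figures assume complete AE ascertainment in all 100 subjects.

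**Illustration of loss**

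Assumption: truncated subjects contribute nothing, so n is the number with complete follow-up. The values of n are assumed, since the documents give no termination rate.

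| n complete | 1 − 0.98^n | 1 − 0.025^(1/n) |
|---|---|---|
| 100 | 86.7% | 3.62% |
| 98 | 86.2% | 3.69% |
| 97 | 85.9% | 3.73% |
| 95 | 85.3% | 3.81% |
| 88 | 83.1% | 4.11% |
| 80 | 80.1% | 4.51% |
| 70 | 75.7% | 5.13% |

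The limit passes 3.7% at the third lost subject. The assumption is severe, because events up to discharge would normally have been seen. If 12 truncated subjects had already passed through half their risk, detection would be 1 − 0.98^88 × 0.99^12 = 85.0%, not 83.1%.

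**How many might be in follow-up at a closure**

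With 100 subjects and up to 8 sites, the average is 100 / 8 = 12.5 per site. That is total enrolment, not the number in follow-up on a given day. Assume even accrual over 6, 12 or 18 months (182.5, 365 or 547.5 days). The expected number within 28 days of surgery at one average site is then:

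- 12.5 × 28 / 182.5 = 1.9
- 12.5 × 28 / 365 = 1.0
- 12.5 × 28 / 547.5 = 0.6

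Closure of all eight sites would affect about eight times as many: 15.3, 7.7 or 5.1.

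**The case against.** The strongest reply is that this is contingency wording in a descriptive post-market study, and that much of the risk is handled elsewhere. Several stronger readings are tempting and do not stand.

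- A reader might infer that all AE data stop at withdrawal. They need not. Section 5.2.1 follows reported SAEs to resolution, stability or exhausted attempts, and 5.2.2 requires AEs to be documented throughout the investigation.
- A reader might infer that 5.2.1 contradicts itself. Its second sentence can be read as a coding rule for events still open, and it does not say that collection ends at the last visit. The wording is ambiguous for early withdrawals, no more.
- A reader might infer that the AE rule, like the termination rule, applies only to exposed subjects. It refers to the subject, not the enrolled subject; it is a matter of judgement; and AE pages are also completed for screen failures (3.2.2). For that rule, post-operative application is a reasonable inference, because recordable AEs must be attributable to the procedure or device (5.1.1), but it is not the literal text.
- A reader might infer that consented subjects awaiting surgery fall into a gap. Section 3.2.2 records them as screen failures.
- A reader might infer that one closure costs about 12 subjects. The calculation above shows why that figure is too high for an average site.

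It is also fair that discontinuations will be visible in SAP Table 1, and that 3.2.5 leaves some termination procedures to the Sponsor. Those procedures are not shown and could include a final contact, but the sentence concerns an Investigator ending one subject's participation, not closure of a site or the study.

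These points narrow the concern. None of them supplies a commitment to a final safety contact after termination or AE withdrawal.

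**Conclusion.** The point holds in limited form. Taken together, 3.2.1 and 3.2.5 mean that termination, including for safety, ends follow-up only in subjects in whom device use was already attempted, and the final-visit commitment does not reach termination or AE withdrawal. What can be lost is new AEs and the outcomes of non-serious AEs between withdrawal and Visit 3.

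The size cannot be fixed from the documents. On the assumed accrual periods, closure of one average site would truncate roughly one or two subjects, fewer than the three at which the stated 3.7% limit is passed. A larger site, faster accrual or several closures could pass it. The binomial figures also treat the loss as unrelated to risk; loss triggered by a safety concern could bias the AE percentages in a way they do not show. The trigger may never occur, but if it does, the affected data belong to the primary safety endpoint. A change of wording is worthwhile.

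**What to change.** In Protocol 3.2.5, extend the commitment to obtain final-visit observations to AE withdrawal and to site or study termination. State that the Visit 3 safety contact will be attempted for every enrolled subject unless consent has been withdrawn, the subject has died, or a regulatory or institutional restriction prevents contact. The last exception is needed because regulatory mandates and institutional non-compliance are themselves listed reasons for closure.

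In Protocol 5.2.1, reconcile the two SAE sentences so that the ongoing status is recorded only after the stated follow-up to resolution, stability or exhausted attempts, for early-withdrawal subjects as well.

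The cost is a protocol amendment, with Sponsor issue, investigator signature and IRB/EC approval, and a few contacts at a closed site. Visit 3 may already be done by telephone, so no new procedure is needed.
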